11.0 Criteria for Removal from the Study

- 11.1 Progressive disease or failure to respond after 2 courses of therapy.
- 11.2 Unacceptable (Grade 3 or 4) toxicity in the absence of significant antileukemic effect.
- 11.3 Patient request; non-compliance.

12.0 Statistical Considerations

12.1 General Description

The overall trial objective is to provide a very early assessment of efficacy (phase II A) of Nivolumab when used in combination with the standard combination of idarubicin and cytarabine. Initially, a small dose escalation trial will determine the dose at which the regimen will be evaluated in the subsequent study of efficacy. Once the combination dose is determined, patients meeting phase II eligibility criteria will be accrued.

12.2 Phase I study

The 3+3 design will be used to identify the MTD of nivolumab. The following table lists out the 3 dosage levels that will be used in the study, and the starting dose is 1mg/kg IV

of Nivolumab With 3 doses, the maximum total number of patients for phase I part will be 12 patients.

The dose of treatment agent, that is, Nivolumab, will be escalated in successive cohorts of patients. Patients will be entered sequentially to each dose level. If none of the first 3 patients at a dose level experience first cycle dose-limiting toxicity (DLT), new patients may be entered at the next higher dose level. If 1 of 3 patients experience first cycle DLT, up to 3 more patients are started at that same dose level. If 1 of 6 experience DLT, then new patients may be entered at the next higher dose level. If 2 or more experience first cycle DLT, no further patients are started at that dose. The MTD is the highest dose level in which <2 patients of 6 develop first cycle DLT.

Table 13.1 Dose levels of nivolumab

Dose level	Nivolumab (mg/kg IV)
-1	0.3
0	1
1	3

Prior to advancing/changing dose levels, a cohort summary will be completed and submitted to the IND Office Medical Monitor for review and approval.

12.3 Phase 2 study

The primary outcome of this trial is event-free survival (EFS) which is defined as the time from the treatment start till treatment failure, relapse, or death whichever comes first.. The treatment failure is defined as not achieving CR after two cycles of treatment. If the patient achieves remission after the treatment, the relapse occurred in the later time would be considered as "event". We will monitor the EFS as patients accrue and are evaluated. The chemo-naïve patients under MTD in phase I will be included in the phase 2 study.

The monitoring uses the Bayesian method of Thall, et al [2005]. It will be assumed that EFS follows an exponential distribution with median m_T under the current treatment. The

historical median of EFS is denoted by m_H given an historical (H) treatment. For priors, we assume the conjugate inverse gamma (IG) priors $m_T \sim \text{IG}(a_T, b_T) = \text{IG}(3.2, 15.6)$ and $m_H \sim \text{IG}(a_H, b_H) = \text{IG}(124.5, 864.5)$. Both priors have mean of 7 months while $\text{var}(m_T) =$

40 and $\text{var}(m_H) = 0.40$. That is, the prior on m_T is non-informative while the prior on m_H is informative. The trial will be monitored and will be stopped early if, based on the data available at the time, it is unlikely that the median EFS rate will be at least 7 months. The monitoring is continuous monitoring starting from the 1st patient.

$\Pr(\text{median EFS under treatment} \geq \text{median EFS under historical treatment} \mid \text{data from the trial}) < 0.03$.

The operating characteristics of this rule for $N_{\text{max}} = 75$ patients, computed assuming a 5 patient/month accrual rate and 24 months of follow up after the last patient is accrued, *The operating characteristics* are given in the following table.

Table 13.2 Operating characteristics. *The operating characteristics for the EFS monitoring rule are summarized in the following table.*

Simulation Results		
Median months to death or relapse	Pr(Stop early)	Mean # pats. (25%, 75% percentiles)
5	0.8	51.3 (31,75)
7	0.11	70.5 (75,75)
9	0.02	73.9 (75,75)

The Department of Biostatistics at MD Anderson will provide and maintain a website (“Clinical Trial Conduct”: <https://biostatistics.mdanderson.org/ClinicalTrialConduct/>) for patients enrolled on this study. The Clinical Trial Conduct website resides on a secure server, and access is gained through usernames and passwords provided to personnel responsible for enrolling patients and updating patient data. The website is accessed through a browser using secure socket layer (SSL) technology. Personnel responsible for enrolling patients on trials, which includes the principal investigator(s), research nurse(s), and data coordinator(s), will be trained by members of the Department of Biostatistics in the use of the trial website; the importance of timely updating of follow-up times and recording of events will be emphasized in training.

We will also monitor the unacceptable nivolumab grade 3 or 4 drug attributable toxicity rate by 12 months, and we will stop the trial if we have statistical evidence that this unacceptable toxicity rate is more than 10%. The method of Thall, Simon and Estey [1995] will be used for toxicity monitoring for this study. The software Multc Lean.Version 2.1 was used to run the simulation.

We will stop the trial early if

$P(\text{unacceptable toxicity by 12 months} > 10\% \mid \text{data from the trial}) > 0.95$.

That is, given the outcomes from the patients who have already been evaluated, if we determine that there is more than a 95% chance that the unacceptable toxicity rate is more than 10%, we will stop the trial. This decision rule gives the following stopping rule. We assume a beta(0.2, 1.8) prior distribution for the unacceptable toxicity rate.

The operating characteristics of this decision rule are shown in Table 2. When the trial is completed we will report the posterior probability that the unacceptable toxicity rate by 12 months is more than 10%, and we will give a 90% credible interval for this rate.

Table 13.3. toxicity stopping boundaries in cohort size of 5.

Number of patients	Stop the trial if there are this many patients achieving toxicity
5	3-5
10	4-10
15-20	5-20
25	6-25
30	7-30
35-40	8-40
45	9-45
50-55	10-55
60	11-60
65-70	12-70

Table 13.4: Operating characteristics for monitoring of toxicity rate.

True toxicity Rate	Early Stopping Probability	Average number of patients treated
0.05	0.01	75
0.1	0.11	70
0.15	0.47	56
0.2	0.83	38

0.25	0.97	25
------	------	----

12.4 Analysis plan:

Demographic and disease characteristics of the patients at registration will be summarized using descriptive statistics such as mean, standard deviation (SD), median and range. Frequency tables will be used to summarize categorical variables. The EFS will be estimated by Kaplan-Merier method, along with the 95% confidence intervals, and logrank test will be used to assess the EFS differences under different patient subgroups. The Cox proportional hazards model will be used to analyze the effects of treatments and other covariates.

Data from all subjects who receive any study drug will be included in the safety analyses.

Subjects who entered the study and did not take any of the study drugs and had this confirmed will not be evaluated for safety. The severity of the toxicities will be graded according to the NCI CTCAE v4.03 whenever possible. We will follow standard reporting guidelines for adverse events. Safety data will be summarized by category, severity and frequency. The proportion of patients with AEs will be estimated, along with the Bayesian 95% credible interval.

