3.0 Objectives

- 3.1 **For phase I portion of study:** To determine the tolerability of the combination of idarubicin, cytarabine (ara-C), and nivolumab (IAN) in patients with high-risk MDS and AML.
- 3.2 **For phase II portion of study:** To determine event-free survival (EFS) where the events is defined as death or relapse using the combination of idarubicin, cytarabine, and nivolumab in patients with high-risk Myelodysplastic syndrome (MDS) and Acute Myeloid Leukemia (AML).

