5.0 Treatment Plan

5.1 **General:** All patients should be registered with PDMS. Information pertaining to important prognostic factors such as age, performance status and prior therapy will be recorded.

5.2 **Treatment Schedule:** (Each cycle is approximately 28-35 days)

a. **Phase I**

Nivolumab dosed as indicated below starting approximately on day 24 ± 2 days

Idarubicin 12 mg/m² IV over 15 to 30 minutes daily x 3 (days 1-3)

ara-C 1.5 g/m² IV over 24 hours daily (days 1-4)

Solumedrol 50 mg or dexamethasone 10 mg IV daily for 3-4 days with ara-C (days 1-4)

All patients may receive a second induction course at the discretion of treating physician.

The dose of investigational agent, that is, Nivolumab, will be escalated in successive cohorts of patients. Patients will be entered sequentially to each dose level. If none of the first 3 patients at a dose level experience first cycle dose-limiting toxicity (DLT), new patients may be entered at the next higher dose level. If 1 of 3 patients experience first cycle DLT, up to 3 more patients are started at that same dose level. If 1 of 6 experience DLT, then new patients may be entered at the next higher dose level. If 2 or more experience first cycle DLT, no further patients are started at that dose. The MTD is the highest dose level in which <2 patients of 6 develop first cycle DLT. The following table lists out the 3 dosage levels that will be used in the study, and the starting dose is 1mg/kg IV of Nivolumab. There will be no intra-patient dose escalation for Nivolumab.

The enrollment of participants will be staggered; all the participants in each cohort will be observed for approximately 3 weeks from the first dose of Nivolumab before proceeding to the next cohort.

Dose of nivolumab will be as follows:

Dose level	Nivolumab (mg/kg IV)	No of patients
-1	0.3	3
0	1	3
1	3	3

b. **Phase II** (Each cycle is approximately 28-35 days)

Patients will receive 1 or 2 induction cycles of therapy according to the following starting schedule:

Nivolumab starting approximately on day 24 \pm 2 days at a dose defined by Phase I portion of the study but it is expected that the dose 3 mg/kg will be selected based on prior studies.

Idarubicin 12 mg/m² IV over 15 to 30 minutes daily x 3 (days 1-3)

ara-C 1.5 g/m² IV over 24 hours daily (days 1-4) (days 1-3 for patients older than 60)

Solumedrol 50 mg or dexamethasone 10 mg IV daily for 3-4 days with ara-C (days 1-4) (days 1-3 for patients older than 60).

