5.6 Myelosuppression

Patients with acute leukemia usually present with abnormal peripheral blood counts at the time therapy is started, and myelosuppression is an expected event during the course of therapy for acute leukemias and myelodysplastic syndromes. Thus, no dose adjustments or treatment interruptions for myelosuppression will be planned for the first 6 weeks of therapy. After this time, treatment interruptions and dose adjustments may be considered according to the following guidelines:

Patients with neutropenia or thrombocytopenia as a consequence of the disease prior to the start of therapy do not require treatment interruptions for myelosuppression. Dose reductions of the chemotherapy agents in these patients should be considered on an individual case basis and discussed with the PI.

Nivolumab is not associated with myelosuppression – it can be held if necessary but no dose reductions are needed after resumption

- 5.7 **Dose adjustments for only one of the drugs** can be made if, in the opinion of the treating physician, the toxicity is attributable to one of the drugs.
- 5.8 Patients who show no significant anti-tumor effect (i.e. no CR or CRp) after 2 courses will be taken off the study.
- 5.9 **Remission Consolidation/Maintenance:** Patients achieving a CR or CRp may receive consolidation maintenance therapy as follows:
 - a. Consolidation – Up to 5 additional courses as follows:
 - Idarubicin 8 mg/m² IV over 15 to 30 minutes daily x 2 days (or the final induction dose, whichever is lower).(days 1-2)
 - Ara-C 0.75 g/m² IV over 24 hours daily x 3 days (or the final induction dose, whichever is lower) (days 1-3)
 - Nivolumab dose as per induction IV every 2 weeks as a continuation of the induction treatment.
 - Solumedrol 50-100 mg or dexamethosone 10 mg IV daily x 3 days with ara-C (days 1-3)
 - courses given every 4-6 weeks upon recovery of counts and toxicities
 - b. Maintenance – Nivolumab will be administered every 2 weeks for up to 1 year with no breaks except for toxicity. Maintenance will only be administered in patients in CR or CRp.
 - c. Consideration of allogeneic transplant in CR. Patients eligible for allogeneic.

SCT will be evaluated for the procedure, if felt to be in their best interest. Therapy with nivolumab will be discontinued at least approximately one week prior to admission for the transplant procedure.

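### The primary endpoint EFS has two definitions (3.2 and the Table 13.2 label against 12.3), and Table 13.2 fits a plain exponential curve, not the 12.3 endpoint

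*Combined protocol and SAP*

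**What the plan says.** - **Objective 3.2:** "To determine event-free survival (EFS) where the events is defined as death or relapse". Treatment failure is not mentioned.
- **Section 12.3, primary outcome:** EFS runs from the start of treatment to the earliest of treatment failure, relapse and death. "The treatment failure is defined as not achieving CR after two cycles of treatment".
- **Table 13.2, in the same section:** the scenarios of 5, 7 and 9 months are labelled "Median months to death or relapse".
- **Model, 12.3:** "It will be assumed that EFS follows an exponential distribution with median m_T".
- **Comparator, 12.3:** the "historical median of EFS is denoted by m_H given an historical (H) treatment". Its prior is IG(124.5, 864.5), with mean 7 months. No source is given.
- **Timing, 5.2:** "Each cycle is approximately 28-35 days", so two cycles end at about day 56-70.
- **Removal, 11.1:** "Progressive disease or failure to respond after 2 courses of therapy". This fits 12.3.
- **CRp, 5.8:** "Patients who show no significant anti-tumor effect (i.e. no CR or CRp) after 2 courses will be taken off the study". Section 5.9 allows maintenance in CR or CRp. Section 9.1 counts CRp as a response, but it counts PR too.

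**The concern.** The two definitions treat a patient who is alive without CR after two courses differently. Under 12.3 that patient has an event near month 2. Under 3.2 the patient cannot relapse, never having remitted, and has an event only at death. EFS is both the primary result and the input to continuous monitoring. The rule and its prior are fixed, so the choice of definition changes how often the trial stops.

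A second problem remains after the wording is aligned. If 12.3 governs, a block of events falls at the end of cycle 2. The monitoring model and Table 13.2 assume a constant hazard.

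Two smaller gaps sit alongside. Read literally, 12.3 scores CRp as failure, while 5.8 and 5.9 treat it as remission. And the table label leaves open whether the 7-month historical figure counts treatment failure.

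**Working it through.** **Rule as simulated (all inputs from 12.3).** With d events and total follow-up T months, the posterior is m_T ~ IG(3.2 + d, 15.6 + ln2 × T), and m_H ~ IG(124.5, 864.5). Stop if Pr(m_T ≥ m_H) < 0.03. N = 75, accrual 5 per month (Poisson), a look at each new entry and a last look 24 months after the last patient.

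**Step 1: reproduce Table 13.2.** Plain exponential event times, 20,000 runs:

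| Median (months) | Pr(stop), simulated | Pr(stop), stated | Mean N, simulated | Mean N, stated |
|---|---|---|---|---|
| 5 | 0.80 | 0.8 | 51.1 | 51.3 |
| 7 | 0.11 | 0.11 | 70.4 | 70.5 |
| 9 | 0.02 | 0.02 | 74.0 | 73.9 |

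The table is right for its stated model.

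**Step 2: put the 12.3 failures in.** A share f has its event at month 2 (56-70 days is 1.84-2.30 months). The rest are exponential from time 0 with hazard h = ln((1 − f)/0.5)/M, so the 12.3 median is still M. The share f is assumed, at 17-35%. The share in remission at month 2 is (1 − f) × exp(−2h). At M = 5:

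- f = 17%: h = ln(1.66)/5 = 0.101, remission share 0.83 × exp(−0.203) = 68%.
- f = 35%: h = ln(1.30)/5 = 0.052, remission share 0.65 × exp(−0.105) = 59%.

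Over all three medians the share is 59-74%, near the 60-70% CR rate in section 2.1 b.

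| Pr(stop) | f = 17% | 20% | 23% | 30% | 35% | Table 13.2 |
|---|---|---|---|---|---|---|
| M = 5 | 0.56 | 0.53 | 0.49 | 0.44 | 0.41 | 0.80 |
| M = 7 | 0.15 | 0.16 | 0.17 | 0.20 | 0.23 | 0.11 |
| M = 9 | 0.05 | 0.07 | 0.08 | 0.12 | 0.16 | 0.02 |

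Monte Carlo standard error is at most 0.004. Moving the scoring day across days 56-70 widens the ranges to 0.30-0.59, 0.12-0.29 and 0.04-0.21.

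**Step 3: why it moves both ways.** The exponential model estimates the median as ln2 × (time at risk)/(events).

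- *Long follow-up, M = 5, f = 17%:* mean event time is 0.17 × 2 + 0.83/0.1014 = 8.53 months, so the estimate tends to 0.693 × 8.53 = 5.9, not 5. The long tail hides a poor regimen, and the rule stops less often.
- *Follow-up only just past month 2, M = 9, f = 17%:* h = 0.0563. Events are 1 − 0.742 = 0.258 per patient. Time at risk is 0.17 × 2 + 0.83 × (1 − exp(−0.1126))/0.0563 = 1.91 months. The estimate is 0.693 × 1.91/0.258 = 5.1, not 9. The early block makes a good regimen look poor, and the rule stops more often.

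**Step 4: same patients, two definitions (15,000 runs, 12.3 median 5 months).** Non-remitters have their event at month 2 (12.3), or at month 2 plus an exponential time with an assumed median of 1, 2, 4 or 12 months (3.2).

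- f = 17%: 0.55 under 12.3, against 0.35, 0.23, 0.11 and 0.04 under 3.2.
- f = 23%: 0.49 under 12.3, against 0.22, 0.10, 0.03 and 0.01 under 3.2.

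**Step 5: conditional only.** Suppose the 7-month historical figure counted death or relapse alone while the trial scored 12.3 events. At a death-or-relapse median of 7 months, Pr(stop) would be 0.16-0.77 (f = 17%) or 0.19-0.94 (f = 23%), over the same 1-12 months. No passage shows that this mismatch exists.

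**The case against.** **Section 12.3 probably governs.** It is the fuller definition and agrees with 11.1, so 3.2 and the label may be shorthand. That is likely, and the fix adopts 12.3. But then Table 13.2 does not describe the endpoint used.

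**The exponential model is declared, and the table is correct under it.** True. The rule may keep that model, but its operating characteristics should be computed for the event pattern that 12.3 creates.

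**Other curves come close to the table.** A 2% failure share nearly reproduces it (0.77/0.11/0.02), and single rows match in other scenarios. The claim that only a plain exponential reproduces the table is therefore limited to the curves tested. But 2% is far below the 30-40% without CR implied by section 2.1 b, and at 5% the 5-month row is already 0.73.

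**The effect on enrolment is modest at low failure shares.** About 0.14 of the stated 0.80 comes from the last look, when all 75 patients are in. During accrual, stopping at 5 months falls from 0.66 to 0.53 at 17% failures, and mean N at 5 months rises only from 51.1 to 54.7-57.2 over the 17-35% range. This stands, though Table 13.2 itself reports the larger figure.

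**The plan gives no scoring day.** Spreading failures evenly over days 28-70 gives 0.62-0.54, 0.20-0.38 and 0.07-0.28 for 17-35% failures, with no extra patients at 5 months. The exact ranges depend on this choice; the direction at 5 and 9 months does not. Scoring from day 28 also sits poorly with a definition that requires two cycles.

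**Steps 4 and 5 assume survival after failure.** No passage supports a value, or says how patients taken off study would be followed. These results illustrate the stake and are not estimates.

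**Conclusion.** The concern holds: the plan is wrong as written. The conflict between definitions is in the text and needs no assumption. Table 13.2 is accurate for a plain exponential curve but does not describe the 12.3 endpoint. With 17-35% of patients failing at month 2, the chance of stopping a regimen with a 5-month median is about 0.41-0.56, not 0.80, and the chance of stopping one with a 9-month median is about 0.05-0.16, not 0.02. At 7 months the change can be small (0.12 against 0.11 at the low end). The direction at 5 and 9 months is firm. The size rests on the assumed failure share and scoring day. A mismatch in the historical median is possible but not shown. Because the primary result and the stopping decision both depend on the definition, this must be fixed.

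**What to change.** 1. Use one definition, that of 12.3, in 3.2, in 12.3 and in the label of Table 13.2, and state the day on which treatment failure is scored.
2. State in 12.3 whether CRp counts as remission for EFS, and reconcile this with 5.8 and 5.9.
3. Give the source of the 7-month historical median and confirm that it and the IG(124.5, 864.5) prior count the same events. If they do not, re-derive the prior.
4. Re-run Table 13.2 with failures clustered near month 2, state the failure share and scoring day assumed, and restate Pr(stop) for all three medians. Aligning the wording alone does not correct the table.

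Cost: a wording amendment, a check (possibly a re-computation) of the historical prior, and one simulation re-run. No extra patients or assessments are needed. The restated operating characteristics will probably be less favourable than those now printed.

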Nivolumab will be administered at approximately 2 week intervals for up to 1 year.

5.3 Dose modifications during phase II:

Patients who experience nivolumab-specific (defined as determined by the principal investigator) grade 3-4 extramedullary toxicities during induction cycle #1, and who are not in CR after cycle #1, may receive a second induction course at a similar or lower dose level with respect to idarubicin and cytarabine. Other dose modification schedules felt to be in the best interest of the patient may be permitted, after discussion with the principal investigator. There will be no dose modifications of idarubicin or cytarabine for either induction cycle #1, or second induction course, secondary to myelosuppression. There will be no dose reduction with respect to Nivolumab but dose delays or interruptions are permitted after discussion with the PI.

5.4 Administration guidelines for nivolumab: Nivolumab will be administered by IV infusion over approximately 60 minutes \pm 10 minutes. The recommended infusion duration for the product is 60 minutes and every effort should be made to adhere to this time as closely as possible.

5.5 No dose reduction is allowed for Nivolumab. Dose delays and interruptions should follow the guidance in section 6.10.3.

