b) Grade 3 hematologic toxicity (criteria for leukemia on the CTC version 3.0) lasting for 6 weeks or more after interruption of therapy with a hypocellular bone marrow and no marrow blasts. Anemia will not be considered a hematologic DLT. As the following are common events in patients with leukemia (> 50%), they will not be used for the definition of MTD and DLT, nor will they be reported as ADRs: prolonged myelosuppression (grade 3 - 4), neutropenic fever without infection (grade 3), non-neutropenic fever (grade 3), infections with grade 3 and 4 neutropenia, infections without neutropenia (grade 3), readmission associated with NCI grade 3 toxicity cytopenias not resulting in death, transfusions of platelets and packed RBCs (grade 3).

5.12

Concomitant medications: In the event of severe anemia, thrombocytopenia or neutropenia, patients may receive appropriate supportive care (e.g., transfusions, prophylactic antibiotics, antifungals and/or antivirals, hematopoietic growth factors). In the event of high white blood cell (WBC) counts, patients may receive hydroxyurea (at any dose) or 1 dose of cytarabine (up to \leq 2g) prior to start of study treatment in order to keep their WBC at an acceptable level while being evaluated for the study. During the trial they may undergo leukopheresis for the same purpose.

Concomitant administration of any other therapy specific for MDS or AML, including any use of systemic retinoids, is prohibited. Concomitant administration of any other anticancer therapy is prohibited. Intrathecal chemotherapy is allowed, when indicated.

Subjects may receive anti-infective prophylaxis according to institutional practices. Use of recombinant myeloid colony stimulating factors (CSF) is allowed, if patients have febrile neutropenia or documented infections.

Concomitant medications will be recorded in the medical records only.

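### EFS treatment failure is defined only after two cycles, so a patient without CR who leaves after one cycle has no event before death, which biases EFS upward and weakens the futility rule

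*Combined protocol and SAP*

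**What the plan says.** Section 12.3 makes EFS the primary phase II outcome, "defined as the time from the treatment start till treatment failure, relapse, or death whichever comes first". Failure is then narrowed: "The treatment failure is defined as not achieving CR after two cycles of treatment". Relapse counts only in a patient who has first reached remission.

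Several provisions let a patient stop before a second cycle without CR:

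- Section 5.2b: "Patients will receive 1 or 2 induction cycles of therapy according to the following starting schedule".
- Section 5.3: patients with nivolumab-specific grade 3–4 extramedullary toxicity "who are not in CR after cycle #1, may receive a second induction course at a similar or lower dose level". The second course is permitted, not required.
- Section 11.2 removes patients for "Unacceptable (Grade 3 or 4) toxicity in the absence of significant antileukemic effect", with no minimum number of courses.
- Section 11.3 allows removal for patient request or non-compliance, again with no minimum.

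Section 5.12 adds: "Concomitant administration of any other therapy specific for MDS or AML, including any use of systemic retinoids, is prohibited". A patient who needs such therapy before CR therefore has to come off study treatment.

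No section makes exit without CR, or the start of other antileukaemic therapy, an EFS event. Section 12.4 names Kaplan-Meier estimation but gives no censoring rule. Section 8.5 describes one history and physical examination at early exit and no later follow-up for EFS.

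**The concern.** A patient who leaves after one cycle without CR is in substance an induction failure. Under 12.3 as worded, that patient contributes event-free time up to death or censoring. The effect goes one way. The median EFS is overstated, and so is Pr(m_T ≥ m_H | data), the quantity monitored from the first patient. The stopping rule exists to catch a regimen with a short EFS, and that is where the lost events matter most.

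The gap is separate from the conflict with Section 3.2, which lists only death and relapse as events. It remains even if 12.3 alone governs.

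**Working it through.** **1. Event status of a one-cycle leaver without CR, read literally**

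| Event in 12.3 | Can it occur? |
|---|---|
| No CR after two cycles | No: two cycles were not given |
| Relapse | No: there was no remission |
| Death | Yes, if the patient is still followed |

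**2. The stopping rule, reproduced first**

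Inputs from 12.3: priors IG(3.2, 15.6) for m_T and IG(124.5, 864.5) for m_H; stop if the probability is below 0.03; at most 75 patients; 5 per month; 24 months of follow-up after the last entry.

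With D events and total follow-up T (months), the posterior of m_T is IG(3.2 + D, 15.6 + ln2 × T). Writing a_T, b_T for these parameters, Pr(m_T ≥ m_H) is the Beta(a_T, 124.5) distribution function evaluated at b_T/(b_T + 864.5). Accrual was simulated as Poisson, with a look at each arrival and one final look.

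| True median (months) | Table 13.2: Pr(stop), mean N | Simulated: Pr(stop), mean N |
|---|---|---|
| 5 | 0.80, 51.3 | 0.80, 50.6–51.0 |
| 7 | 0.11, 70.5 | 0.11–0.12, 70.2–70.5 |
| 9 | 0.02, 73.9 | 0.02, 73.9 |

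The model of the rule therefore matches the plan's own.

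**3. Adding early leavers**

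Assumptions, because the documents give no figures:

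- A share f leaves without CR at day 32, near the middle of the 28–35-day cycle (32/30.4 = 1.05 months).
- All other patients have exponential EFS at rate r, set so that the true median is 5 months when exit is scored as an event: r = ln(2(1 − f))/5.
- Median survival after exit is 3, 6 or 12 months.

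For f = 10%, r = ln(1.8)/5 = 0.1176 per month. Censoring leavers at exit gives an apparent median of ln2/0.1176 = 5.9 months. Following them to death, with post-exit median s, the apparent median x solves f·exp(−ln2·(x − 1.05)/s) + (1 − f)·exp(−r·x) = 0.5. For s = 6 this gives x = 6.0.

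Apparent median EFS in months, with Pr(stop) after the semicolon:

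| f | Exit scored as event | Censored at exit | Followed to death, s = 3 / 6 / 12 |
|---|---|---|---|
| 5% | 5.0; 0.76 | 5.4; 0.56 | 5.3 / 5.5 / 5.6; 0.64 / 0.56 / 0.47 |
| 10% | 5.0; 0.73 | 5.9; 0.30 | 5.6 / 6.0 / 6.4; 0.46 / 0.31 / 0.21 |
| 20% | 5.0; 0.70 | 7.4; 0.04 | 6.3 / 7.3 / 8.3; 0.16 / 0.05 / 0.03 |

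A second simulation of the rule gave 0.78 falling to 0.56–0.58 at 5%, and 0.71 falling to 0.29–0.32 at 10%. In a trial of 75, these shares are about 4 (0.05 × 75 = 3.75) and 7 or 8 (0.10 × 75 = 7.5) patients. The first results column lies below 0.80 because a cluster of early events makes EFS non-exponential.

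**4. How large f could be**

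Section 2.1b gives CR rates of 60–70%, so 30–40% have no CR. That group includes induction deaths, which are already events. In the cohort aged 65 or older described there, 245 − 118 = 127 had no CR and 54 of them (about 42%) died in induction. Applied as an illustration, this leaves 0.30 × 0.58 = 17% to 0.40 × 0.58 = 23% alive without CR. The 20% row would need most or all of these patients to leave after one cycle, so the 5% and 10% rows are the ones to rely on.

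**The case against.** The strongest reply is that one-cycle exit without CR is the exception. Sections 5.8 and 11.1 set removal for non-response at two courses, and 5.3 offers a second induction even after nivolumab toxicity. The range of one or two cycles in 5.2b may simply mean one if CR is reached and two if not. The two-cycle wording in 12.3 could also be a deadline, so that anyone ending induction without CR has failed. These points limit how often the problem arises. They do not settle how such a patient is scored, and the text never states the deadline reading.

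Three stronger inferences are not supported:

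- A reader might infer that these patients have no event at all. Death remains an event.
- A reader might infer that rescue therapy necessarily lengthens EFS. That needs follow-up beyond exit. If patients are censored at exit, rescue adds no time and the bias comes from informative censoring. The documents specify neither, and they do not mention rescue therapy for these patients.
- A reader might assume that a quarter to a half of all patients without CR leave early, and infer that the reported median would cross 7 months. No passage supports such a rate, and the group without CR includes induction deaths.

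The documents also do not say how early non-responders were scored in the historical 7-month median. If they were scored in the same loose way, the comparison with m_H may be less biased than the estimate of m_T.

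**Conclusion.** The gap is real and affects the primary endpoint. The plan gives a patient without CR who leaves after one cycle no event before death, and either way of handling that patient overstates EFS relative to scoring the exit as a failure. At a true median of 5 months, 5% early leavers cut the chance of stopping from about 0.76–0.78 to about 0.56–0.58, and 10% cut it from about 0.71–0.73 to about 0.29–0.32. Over post-exit medians of 3 to 12 months the reduced values range over 0.47–0.64 and 0.21–0.46.

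The direction follows from the definition. The size depends on the assumed leaving share, exit time, post-exit survival and exponential EFS in the other patients. For the comparison with m_H, it also assumes that historical early failures were counted as events.

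**What to change.** In Section 12.3:

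- Define treatment failure as no response by the end of the last induction cycle received, whether one or two. Handle CRp consistently with 5.8 and 5.9: those sections keep CRp patients on treatment, whereas 12.3 names CR alone.
- Date failure at the earliest of: the marrow assessment that ends induction without response; removal for toxicity or lack of effect without response; or the first day of non-protocol antileukaemic therapy given before response.
- For withdrawal by request or non-compliance without new therapy, continue follow-up for events where consent allows and otherwise censor. Add a sensitivity analysis that counts these withdrawals as events, so that the main analysis does not score every withdrawal as leukaemia failure.

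Record the start date of the first off-protocol antileukaemic therapy, and use the same rule in the Clinical Trial Conduct entries. Align Section 3.2 with 12.3. Confirm that the historical 7-month median uses the same event definition.

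The change affects endpoint scoring only, not patient management. It costs a few sentences, one date field and a check of the historical data, with no added patients or procedures. Reported EFS may be slightly shorter. Table 13.2 should be rerun: with exit scored as an event and a true median of 7 months, the same simulation stops with probability 0.15 at f = 5% and 0.20 at f = 10%, against the 0.11 in the table.
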